3.4 Other assessment

3.4.1 Lesions counts on the face and on the trunk

At Screening and Baseline visits, lesion counting will be performed separately on the face and on the upper truncal region.

Specific requirements for children between 9 and 11 years old who do not have moderate acne on the trunk at Screening and/or Baseline (i.e. who do not have PGA of 3, at least 20 inflammatory lesions on the trunk and at least 20 non-inflammatory lesions on the trunk):

The truncal lesion counts will not be performed.

3.4.2 Photographs (at selected sites)

Facial and truncal photos will be taken according to a standardized procedure guideline at selected sites at Baseline, Week 12, Week 26 and Week 52/ET visits to document the effect observed on efficacy areas.

3.4.3 Dermatology Life Quality Index (DLQI) / Children's Dermatology Life Quality Index (C-DLQI)

The Dermatology Life Quality Index (DLQI, designed for use in adults, i.e. subjects over the age 16 years old) and Children's Dermatology Life Quality Index (C-DLQI, designed for 16 years or younger at the date of Baseline visit) will be completed at Baseline and Week 12, Week 26 and Week 52/ET visits.

The DLQI/ C-DLQI will measure the dermatology-related limitations of functional ability and the frequency, severity and impact of acne symptoms on subjects' lives and acne-related quality of life. The six areas addressed in the questionnaire are: symptoms and feelings; daily activities; leisure; work/school; personal relationships; and treatment. The score on the DLQI/ C-DLQI has a possible range of 0 to 30 and can also be presented as a percentage of the maximum possible score of 30.

4 EFFICACY AND SAFETY ENDPOINTS

4.1 Efficacy endpoints

Efficacy endpoints include:

1. Success rate of IGA (defined as 0=clear or 1=almost clear) at each time point
2. Success rate of PGA (defined as 0=clear or 1=almost clear) at each time point
3. Grade change from baseline of IGA at each time point
4. Grade change from baseline of PGA at each time point
5. Subject' s assessment of facial acne improvement at each time point

4.2 Safety endpoints

Safety endpoints include:

1. Local tolerability (erythema, scaling, dryness, and stinging/burning) on the face and trunk,
2. Adverse event,
3. Laboratory parameters
4. Vital signs and physical examination

4.3 PK parameters

PK(Pharmacokinetic) parameters include:

1. C 4 hours
2. Extrapolated AUC0-24h using the linear correlation between AUC0-24h and C 4 hours

4.4 Other endpoints

Other endpoints include:

1. Dermatology Life Quality Index (DLQI) / Children's Dermatology Life Quality Index (CDLQI)

5 POPULATIONS ANALYZED

As this study is a long-term safety study, only the safety population will be used for all statistical analyses.

The safety (SAF) population will be used for the analyses of IGA data and all safety data except for the local tolerability on the trunk.

The safety population on the trunk (SAFT) will be used for the analyses of the local tolerability on the trunk.

The safety population for the PGA (SAFP) will be used for the analyses of the PGA data.

In the case that the SAFT turns out to be identical to the SAF population, then all safety analyses will be based on the SAF population. In the case that the SAFP turns out to be identical to the SAF population, then the analyses of all IGA and PGA data will be based on the SAF population.

PK evaluable subjects in the SAF population will be used for the analysis of PK data.

5.1 Safety (SAF) Population

The SAF Population is defined as subjects who applied the study drug(s) at least once.

5.2 Safety (SAFT) Population on the Trunk

The SAFT population is defined as any subjects in the SAF population who also applied the study medication on the upper truncal region and /or on the middle and lower back at least once.

5.3 Safety (SAFP) Population for the analysis of PGA

The SAFP population is defined as any subjects in the SAF population with moderate truncal acne at Baseline visit. In practice, this excludes from the SAF population the children between 9 and 11 years old who do not have PGA of 3, at least 20 inflammatory lesions on the upper truncal region and at least 20 non-inflammatory lesions on the upper truncal region at study entry.

6 SAMPLE SIZE CONSIDERATION

Approximately 600 subjects will be screened to enroll 450 subjects worldwide, including the United States of America and Europe.

The exposure of subjects to CD5789 50 μ g/g cream follows internationally accepted guidelines for the assessment of clinical safety for products intended for chronic use. The International Conference on Harmonization E1a Guideline suggests that 300 subjects for six months or 100 subjects for one year should be evaluated for safety. This study was designed to ensure that at least 300 subjects will be exposed to CD5789 50 μ g/g cream for 6 months, and 100 subjects exposed for 1 year.

7 STATISTICAL METHODS AND DATA CONSIDERATIONS

For statistical analyses purpose, baseline is defined as the last measurement prior to the first application of the study drug.

No inferential statistical analysis is planned. Data to be collected will be summarized as observed.

For the summary statistics, the categorical variables will be summarized by frequency and percentage for each response category (N, %); and the continuous variables will be summarized using means, medians, minimum, maximum, and standard deviations.

All efficacy variables, DLQI/ C-DLQI, local tolerability, laboratory tests and vital signs will be summarized and analyzed by analysis visit. The methodology for defining analysis visit is provided in Section 7.9 “Analysis visit definition”.

SAS version 9.3 or above will be used for all statistical analyses.

7.1 Study subjects

7.1.1 Disposition of subjects

Disposition of subjects will be summarized based on SAF population. Number and percentage of subjects screened, enrolled, completed, discontinued, and the primary reason for discontinuation based on the CRF exit form will be displayed.

In addition, the number and percentage of subjects in each study population (i.e., SAF, SAFT, SAFP) will be summarized.

7.1.2 Demographic and baseline characteristics

The following demographics variables will be summarized for SAF population: Age, Ethnicity, Race, Skin phototype, and Gender. Age will be analyzed as a continuous variable and will be tabulated by age groups of “<18years” (“9-11 years”, “12-14 years”, “15-17 years”), “18-64 years” (“18-25 years”, “26-35 years”, “36-45 years”, “46-64 years”) and “≥65 years”.

Baseline IGA, PGA and Acne presence on back (middle/lower) will be summarized using SAF population. Facial lesion counts (inflammatory and non-inflammatory) will be summarized using SAF population and truncal lesion counts (inflammatory and non-inflammatory) will be summarized using SAFP population.

7.2 Protocol deviations

Not applicable.

7.3 Medical history, previous and concomitant therapies and procedures

For statistical analysis purposes, previous therapies/procedures are defined as those ending at or before the date of first dose; and concomitant therapies/procedures are defined as those ongoing at the date of first dose or starting after the date of first dose.

Previous and concomitant therapies will be coded using WHODRUG dictionary. Previous and concomitant procedures will be coded using MedDRA dictionary.

A summary table will be provided for each of the following in the SAF population:

1. number and percentage of subjects who had previous therapies/medications by ATC text and WHO drug name
2. number and percentage of subjects who had concomitant therapies/medications by ATC text and WHO drug name
3. number and percentage of subjects who had previous procedures by System organ class and preferred term
4. number and percentage of subjects who had concomitant procedures by System organ class and preferred term

7.4 Efficacy analysis

The safety population for the PGA (SAFP) will be used for the analyses of the PGA data. All other efficacy data will be analyzed based on the SAF population.

7.4.1 Success rate of IGA at each time point

A subject will be considered a success if they achieve an IGA score of 'clear' or 'almost clear'. The success rate will be calculated as the number of successes divided by the number of subjects in the SAF population. The descriptive statistics will be summarized by visit.

7.4.2 Success rate of PGA at each time point

A subject will be considered a success if they achieve a PGA score of 'clear' or 'almost clear'. The same summary statistics as section 7.4.1 will be provided using SAFP population.

7.4.3 Grade change from baseline of IGA at each time point

Raw grade at each visit and grade change from baseline at each post-baseline visit will be summarized as both categorical and continuous variables. In the grade change from baseline analysis, only subjects with both baseline and post-baseline will be included.

7.4.4 Grade change from baseline of PGA at each time point

The same summary statistics as section 7.4.3 will be provided using SAFP population.

7.4.5 Subject's assessment of facial acne improvement at each time point

Subject's assessment of facial acne improvement at each time point will be summarized as both categorical and continuous variables.

7.4.6 Statistical and analytical issues

7.4.6.1 Handling of dropouts or missing data

In this study, summary statistics will be based on the observed data and no missing data imputation will be performed.

7.4.6.2 Interim analyses and data monitoring

No interim analysis is planned for this study.

7.4.6.3 Examination of Subgroups

Subgroup summaries will be provided by descriptive statistics for success rate of IGA (using SAF) and PGA (using SAFP), within each category of the following classification variables:

- Age Group [<18 years (“9-11 years”, “12-14 years”, “15-17 years”), 18-64 years (“18-25 years”, “26-35 years”, “36-45 years”, “46-64 years”) and ≥ 65 years”]
- Gender (female, male)
- Race (white, non-white)
- Country (Europe, USA)
- Skin Phototype (I-III, IV-VI)

7.5 Safety analysis

All safety data will be analyzed based on the SAF population except for the local tolerability on the trunk. The SAFT population will be used for the analyses of the local tolerability on the trunk.

7.5.1 Extent of exposure

7.5.1.1 Study Duration

Study duration (day) is defined as the date of the last visit minus the date of the baseline visit plus one. Study duration will be summarized by descriptive statistics.

7.5.1.2 Treatment Duration

Treatment duration (day) is defined as “the date of the last application on face or the trunk, whichever is later, minus the date of the first application on face or the trunk, whichever is earlier, plus one”. If the date of the last application is not available, the date of the last visit will be used in calculation. If the date of the first application is not available, the date of the Baseline visit will be used in calculation.

Treatment duration will be summarized by descriptive statistics.

7.5.1.3 Study Medication Usage and Treatment Compliance

The study medication usage will be assessed based on CRF data in terms of the number of applications applied.

Number of applications applied is calculated as the expected number of applications minus the total number of missed applications during the treatment. If the number of missed applications is unknown, then 50% doses will be assumed to be missed between two adjacent visits. The expected number of applications is defined as the planned total number of applications during the exposed period. Number of applications applied and the daily average applications applied will be summarized.

Treatment compliance (%) is defined as (the Number of applications applied over the expected number of applications) *100%.

Study medication usage based on number of applications may also be summarized for the face using SAF population and for the trunk using the SAFT population separately.

Additionally, the study medication usage will be assessed based on the returned tubes. Total medication usage weight (g) and daily medication weight (g/day) will be calculated for each subject and be summarized by descriptive statistics.

Total medication usage (g) = total dispensed weight (g) - total returned weight (g);

Daily medication usage (g/day) = total medication usage (g) / study duration (day).

The tubes that were dispensed but not returned will be considered no information and will not be included in the calculation. If all dispensing tubes for a subject are not returned, the subject's total returned weight and daily medication usage will be considered missing.

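### Grams per day are divided by study duration instead of treatment duration, which understates daily use for subjects whose last application precedes their last visit (minor)

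*SAP*

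**What the plan says.** Section 7.5.1 of the SAP defines two lengths of time for each subject.

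- **Study duration (7.5.1.1):** "Study duration (day) is defined as the date of the last visit minus the date of the baseline visit plus one".
- **Treatment duration (7.5.1.2):** the span from first to last application plus one day, ending at "the date of the last application on face or the trunk, whichever is later". There are fallbacks for missing dates, among them: "If the date of the last application is not available, the date of the last visit will be used in calculation".

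Section 7.5.1.3 then gives two kinds of usage measure.

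- **By count:** applications applied and compliance are set against an expected number. "The expected number of applications is defined as the planned total number of applications during the exposed period".
- **By weight:** "Total medication usage (g) = total dispensed weight (g) - total returned weight (g"), and from this "Daily medication usage (g/day) = total medication usage (g) / study duration (day").

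The weight-based rate thus uses the visit-based duration. The SAP gives no reason for this and makes no correction for untreated days. Unreturned tubes have their own rule in the same section: "The tubes that were dispensed but not returned will be considered no information and will not be included in the calculation".

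**The concern.** Cream is used only between the first and the last application. If a subject stops treatment and is seen again later, the days in between lengthen the denominator but cannot add grams to the numerator. A first application after the baseline date has the same effect at the other end. The error always runs downward. It does not depend on unreturned tubes, since it remains when every tube is weighed.

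The two usage measures in 7.5.1.3 also appear to rest on different time bases: exposed time for counts, study time for grams. Section 9 lists a single table for usage and compliance, so the two are likely to stand side by side.

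At stake is the accuracy of a reported exposure figure in a study whose primary objective is long-term safety. The subjects affected are those who stop before their last visit. These may include subjects with related cutaneous events leading to permanent discontinuation, which section 7.5.3 makes events of special interest.

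**Working it through.** **Inputs from the SAP.** The grams formula and the g/day formula come from 7.5.1.3, study duration from 7.5.1.1, treatment duration from 7.5.1.2, and the Week 52 target of Day 365 from Table 3 in 7.9. The SAP states no expected g/day and no gap between last application and last visit, so there is no figure of its own to reproduce.

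**Assumptions.** All tubes are returned, the first application is on the baseline date, and the gap lengths are illustrative.

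**Formula.** Let G be total grams, T treatment duration and S study duration.

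- SAP value: G / S
- Average over the treated period: G / T
- Ratio: (G / S) / (G / T) = T / S
- Relative understatement: 1 - T / S, which is above zero whenever T < S and does not depend on G

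**Results.**

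| Last application | Assumed gap to last visit | T | S | Understatement, 1 - T/S |
|---|---|---|---|---|
| Day 60 | 7 days | 60 | 67 | 10.4% |
| Day 60 | 14 days | 60 | 74 | 18.9% |
| Day 60 | 28 days | 60 | 88 | 31.8% |
| Day 180 | 3 days | 180 | 183 | 1.6% |
| Day 180 | 14 days | 180 | 194 | 7.2% |
| Day 180 | 30 days | 180 | 210 | 14.3% |
| Day 351 | 14 days | 351 | 365 | 3.8% |
| Day 364 | 1 day | 364 | 365 | 0.3% |

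In grams, a subject using an assumed 2.0 g/day up to Day 180 uses 2.0 × 180 = 360 g. With a last visit on Day 194, the SAP formula gives 360 / 194 = 1.86 g/day.

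**Effect on the cohort mean.** If a share p of subjects is understated by u, and all subjects have the same rate while on treatment, the mean falls by p × u. With u = 19%:

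- p = 10%: 0.10 × 19% = 1.9%
- p = 30%: 0.30 × 19% = 5.7%

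Both p and u are assumed. The median would probably move less, because subjects treated up to the last visit are almost unaffected.

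**The case against.** Several points on the other side have weight.

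1. **No planned analysis uses g/day as an explanatory variable.** A reader might infer that the formula hides a relation between amount applied and intolerance. The SAP does not support that. Local tolerability (7.5.2) and adverse events (7.5.3) are broken down by age, race, gender, country and skin phototype, not by grams. Section 9 lists no table of tolerability or events by usage, and section 7 rules out inferential analysis. Masking would matter only if someone related usage to tolerability post hoc. This point stands and limits the consequence.

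2. **The size is unknown.** The gap is not stated, and the percentage is largest for an early stop. Understatements of 50% or more arise if a subject stays in the study for months off treatment (T = 183 and S = 365 gives 49.9%), but the SAP does not say that this happens. It provides for early termination visits without showing how soon they follow the last application. This stands too.

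3. **The information is not lost.** Treatment duration is summarised separately, usage is listed by subject, and the formula names its denominator. The rate per treated day could be recalculated wherever application dates exist. That is true, but it leaves the planned figure as it is.

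4. **Dividing by treatment duration does not give a true daily dose either.** Treatment duration includes interruptions, and a missing last application date is replaced by the last visit date. This is correct and limits what the fix achieves.

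5. **The clash with the count-based measure is partly inferred.** The exposed period is not defined in 7.5.1.3 or equated with treatment duration. The denominator error does not depend on this comparison.

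None of these points gives a reason to prefer study duration.

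**Conclusion.** The point holds as a minor one. With all tubes returned, the g/day value in 7.5.1.3 is too low by exactly 1 - (treatment duration / study duration) for any subject with untreated days between baseline visit and last visit. Under an assumed 14-day gap this is 19% for a stop on Day 60 and 7% for a stop on Day 180. It is close to zero for subjects treated up to the last visit. The overall mean probably shifts by a few percent at most, on the assumed shares shown above.

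The damage is confined to the descriptive exposure summary and subject-level usage. The targets of 300 subjects for six months and 100 for one year, the adverse event incidences, the tolerability summaries and the efficacy results do not use this figure.

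**What to change.** In 7.5.1.3, change the definition to: Daily medication usage (g/day) = total medication usage (g) / treatment duration (day), with treatment duration as defined in 7.5.1.2. Add two notes:

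- The result is an average over the treated period, including any interruptions.
- Where the last application date is missing, the fallback to the last visit leaves the end gap uncorrected.

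If the sponsor wishes to keep the present figure, show both and label the present one as grams per study day.

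The cost is one line of SAP wording and a change of denominator in one derivation. Treatment duration is already derived, and no new data are needed. The rule on unreturned tubes is a separate matter that this change does not touch.

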9 TABLE SHELLS AND REPORTING OUTPUT (GENERAL FEATURES)

The tentative list of tables to be produced in the reporting of this study is shown below. All eCRF data will also be available as subject listings and the eCRF data will be available in CDISC compliant data set.

Demographic and Baseline Characteristics tables

- Summary of Subject Enrollment
- Summary of Subject Enrollment by Analysis Center/Site, SAF Population
- Summary of Subject Disposition, SAF Population
- Summary of Subject Disposition by Analysis Center/Site, SAF Population
- Summary of Subject Disposition by Study Duration, SAF Population
- Listing of Discontinued Subjects, SAF Population
- Summary of Subject Demographics and Baseline Characteristics, SAF Population
- ATC Class, WHO Drug and Drug Name, SAF Population
- Summary of Previous Therapy, SAF Population
- Summary of Concomitant Therapy, SAF Population
- System Organ Class, Preferred Term and Procedure/Non-drug Therapy, SAF Populations
- Summary of Previous Procedure / Non-Drug Therapy, SAF Population
- Summary of Concomitant Procedure/Non-drug Therapy, SAF Population

Efficacy tables

- Summary of Success Rate of Investigator's Global Assessment, SAF Population
- Summary of Success Rate of Physician Global Assessment, SAF Population
- Summary of Investigator's Global Assessment, SAF Population
- Summary of Physician Global Assessment, SAF Population
- Summary of Subject Self-Assessment of Acne, SAF Population
- Summary of Dermatology Life Quality Index (DLQI) Total Score, SAF Population
- Summary of Children Dermatology Life Quality Index (CDLQI) Total Score, SAF Population
- Summary of Dermatology Life Quality Index (Adult and Child) Total Score, SAF Population
- Summary of Dermatology Life Quality Index (DLQI) by Dimension, SAF Population

- Summary of Children Dermatology Life Quality Index (CDLQI), SAF Population
- Summary of Success Rate of Investigator's Global Assessment by Gender, SAF Population
- Summary of Success Rate of Investigator's Global Assessment by Race, SAF Population
- Summary of Success Rate of Investigator's Global Assessment by Age, SAF Population
- Summary of Success Rate of Investigator's Global Assessment by Country, SAF Population
- Summary of Success Rate of Investigator's Global Assessment by Skin Phototype, SAF Population
- Summary of Success Rate of Physician Global Assessment by Gender, SAF Population
- Summary of Success Rate of Physician Global Assessment by Race, SAF Population

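### For a subject who returns some but not all used tubes, total grams and g/day are too low, and the usage summary does not show how many subjects this affects

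*SAP*

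**What the plan says.** Section 7.5.1.3 of the SAP gives two measures of use: a count of applications, and a weight based on returned tubes. For the weight, total usage is dispensed weight minus returned weight, and the rate is "Daily medication usage (g/day) = total medication usage (g) / study duration (day". The denominator comes from section 7.5.1.1: "Study duration (day) is defined as the date of the last visit minus the date of the baseline visit plus one".

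Two rules cover tubes that do not come back:

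- For any such tube: "The tubes that were dispensed but not returned will be considered no information and will not be included in the calculation".
- For a subject who returns nothing: "If all dispensing tubes for a subject are not returned", the subject's "total returned weight and daily medication usage will be considered missing".

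No rule covers a subject who returns some tubes and not others. Section 7 states that "No inferential statistical analysis is planned" and that data are summarised as observed. Section 9 lists one usage and compliance summary table for the SAF population and a subject listing of medication usage. It specifies no count of subjects with incomplete returns.

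**The concern.** An observed rate needs a numerator and a denominator that cover the same period. Here an unreturned tube's grams leave the numerator while the days on which it was used stay in the denominator. The tube is described as carrying no information, yet in effect it enters the subject's result as 0 g used. Total grams has the same shortfall, with no denominator involved.

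Tube weight is the only weight-based measure of use in the SAP, and the trial's primary objective is long-term safety. A reader of the summary table would take grams and g/day as the amount of cream used. As specified, the table does not show how many of its values are too low. Section 7 also reports the minimum, which one subject with mostly unreturned tubes could set.

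**Working it through.** The SAP states no figure for grams used, so there is no figure to reproduce. The check applies the SAP's own formulas.

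**Formulas.** Let *D* be study duration (section 7.5.1.1).

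- True total = sum over all tubes of grams used; true rate = true total / *D*.
- SAP total = the same sum over returned tubes only (section 7.5.1.3); SAP rate = SAP total / *D*.
- Relative error of both = -(grams used from unreturned tubes) / (true total).
- With *n* equally used tubes, *m* of them unreturned and 0 < *m* < *n*, the error is -*m*/*n*.

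**One subject.** Assumed, because the SAP gives neither: 12 tubes with 45 g used from each. *D* is taken as 365 days. True use is 12 × 45 = 540 g, or 540/365 = 1.479 g/day.

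| Unreturned | SAP total (g) | SAP g/day | Error |
|---|---|---|---|
| 1 of 12 | 495 | 1.356 | -8.3% |
| 2 of 12 | 450 | 1.233 | -16.7% |
| 3 of 12 | 405 | 1.110 | -25.0% |
| 6 of 12 | 270 | 0.740 | -50.0% |
| 11 of 12 | 45 | 0.123 | -91.7% |
| 12 of 12 | missing | missing | – |

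The percentages do not depend on grams per tube. With 6 tubes, 1 unreturned gives -1/6 = -16.7%. If the unreturned tube was never used, the error is 0. The row for 11 of 12 is kept as a valid value; only the last row triggers the missing rule.

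**Source of the g/day error.** If the days covered are proportional to tubes, dividing by only the days covered by returned tubes gives, for 1 unreturned, 495 / (365 × 11/12) = 1.479 g/day, which is the true rate. The g/day error is thus the mismatch between numerator and denominator.

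**The cohort mean.** Two assumed cases show that its direction is not fixed.

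- *Equal true use, each used tube unreturned independently with probability q, averaged over subjects with at least one return.* The mean is too low by about *q*: 1.0%, 3.0% or 5.0% for *q* = 1%, 3% or 5%.
- *Unequal use.* 400 subjects use 540 g each, recorded 3% low, so the reported mean is 540 × 0.97 = 523.8 g. Another 50 stop early after 20 g, return nothing and are missing. The true mean over 450 is (400 × 540 + 50 × 20)/450 = 482.2 g. The reported mean is 523.8/482.2 - 1 = 8.6% too high.

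**Size of a complete-return subset.** The share is (1 - *q*)^*n*, applied to the 450 planned subjects in section 6. For *q* = 1%, 3%, 5% this gives 399, 312, 243 subjects with 12 tubes each, and 424, 375, 331 with 6 tubes each.

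**The case against.** The strongest reply is that this is an openly stated convention for a supplementary measure. It feeds no endpoint in section 4, no inference is planned, and section 9 says "All eCRF data will also be available as subject listings", so an affected subject can be found. All of that is true and is why the point is minor. It does not make the values right: the rule is written in this SAP, and followed exactly it returns a number that is too low and presents it as complete.

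A second reply is that dividing by the full duration causes the g/day error, so the denominator should be changed. In the equal-use example that works. It would need days to be attributed to each tube, which the SAP does not define, and it would do nothing for total grams. Leaving the denominator and disclosing the returns is the simpler course.

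Three stronger readings are tempting, and the SAP does not support them:

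- A reader might infer that the all-subject summary is a lower bound. The 523.8 g against 482.2 g example shows that a mean can be too high, because subjects with no returns drop out. Standard deviations are not bounded either: with equal true use the true SD is 0, while partial returns make the recorded SD positive.
- A reader might infer that total usage is undefined when nothing is returned. Total usage is dispensed minus returned weight, and returned weight is set to missing in that case, so the total is missing by implication.
- A reader might infer that compliance or adverse-event rates are affected. Compliance uses application counts and adverse-event incidence uses numbers of subjects at risk (section 7.5.3). Neither uses tube weights.

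**Conclusion.** The point holds for individual subjects. Where some but not all tubes are unreturned and at least one of the unreturned tubes was used, total grams and g/day are too low by the share of true use from those tubes. The direction follows from sections 7.5.1.1 and 7.5.1.3 alone and needs no assumption.

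The size cannot be found from the SAP. The -8.3% for 1 of 12 tubes, and the other percentages, rest on assumed tube counts and equal use per tube. The direction of the error in the cohort mean is not determined. Application counts, compliance and adverse-event rates are unaffected. This is a minor correction to a descriptive table.

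**What to change.** In section 7.5.1.3 and the *Summary of Study Medication Usage and Compliance* table:

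1. Report the numbers of subjects with complete, partial and no tube returns.
2. Summarise total grams and g/day for subjects with complete returns, alongside the all-subject values.
3. Flag individual total grams and g/day as minimum values for subjects with partial returns. Add a footnote that the all-subject summary includes such values and excludes subjects with no returns.

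Do not label the all-subject statistics as a lower bound. The study-duration denominator can stay as written.

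The cost is a few sentences and minor programming. The only data needed are each tube's return status, which the existing exclusion rule already uses. The drawback is that the complete-return summary has fewer subjects, possibly many fewer (243 of 450 in the least favourable assumed case). It may also under-represent longer-treated subjects, who would be expected to receive more tubes. That is why both summaries should be shown.
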